9.2 Sample Size/Accrual Rate

The planned sample size for both the phase 1b/2 portions is between 6 and 37 patients, and the planned accrual rate is 1/month/site (4-6 monthly across ETCTN) based on data from similar trials completed by our organization during the previous 5 years.

PLANNED ENROLLMENT REPORT, PHASE 1b

| Racial Categories | Ethnic Categories | | | | Total |
|---|------------------------|----------|--------------------|----------|-----------|
| | Not Hispanic or Latino | | Hispanic or Latino | | |
| | Female | Male | Female | Male | |
| American Indian/ Alaska Native | 0 | 0 | 0 | 0 | 0 |
| Asian | 0 | 0 | 0 | 0 | 0 |
| Native Hawaiian or Other Pacific Islander | 0 | 0 | 0 | 0 | 0 |
| Black or African American | 1 | 1 | 0 | 0 | 2 |
| White | 4 | 4 | 1 | 1 | 10 |
| More Than One Race | 0 | 0 | 0 | 0 | 0 |
| Total | 5 | 5 | 1 | 1 | 12 |

PLANNED ENROLLMENT REPORT, PHASE 2

| Racial Categories | Ethnic Categories | | | | Total |
|---|------------------------|-----------|--------------------|----------|-----------|
| | Not Hispanic or Latino | | Hispanic or Latino | | |
| | Female | Male | Female | Male | |
| American Indian/ Alaska Native | 0 | 0 | 0 | 0 | 0 |
| Asian | 0 | 0 | 0 | 0 | 0 |
| Native Hawaiian or Other Pacific Islander | 0 | 0 | 0 | 0 | 0 |
| Black or African American | 2 | 2 | 0 | 0 | 4 |
| White | 8 | 10 | 1 | 2 | 21 |
| More Than One Race | 0 | 0 | 0 | 0 | 0 |
| Total | 10 | 12 | 1 | 2 | 25 |

PHS 398 / PHS 2590 (Rev. 08/12 Approved Through 8/31/2015)

OMB No. 0925-0001/0002

9.3 Analysis of Secondary Endpoints

Secondary endpoints we are evaluating are:

- Toxicity frequencies for each patient, according to CTCAE v5
- Time to hematologic count recovery will be analyzed using lab evaluation of complete blood counts and differential
- Differential blast counts between screening and day 8 will be analyzed using lab evaluation of complete blood counts and differential
- Rate of MRD positivity will be evaluated by multiparameter flow cytometry, next-generation sequencing (or both) after induction therapy among those patients who attain morphologic and cytogenetic CR
- Progression free survival for all patients, defined as the time from the start of study treatment until progression or death, whichever occurs earliest. Patients will be censored at earliest of loss to follow-up, allogeneic stem-cell transplantation, or initiation of other anti-leukemia therapy when in remission
- Overall survival for all patients

Every report will contain all patients included in the study. For the response calculation, the report will contain at least a section with all eligible patients. Another section of the report may detail the response rate for evaluable patients only. The maximum grade for each type of toxicity will be recorded for each patient, and frequency tables will be reviewed to determine toxicity patterns. CR rate and Rate of MRD positivity will be calculated with the exact binomial 95% confidence intervals. The Kaplan-Meier method will be used to estimate time to progression and overall survival.

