Treatment plan: Pinometostat will be given IV starting on day 1 at one of two doses in the phase 1b portion, and at a single defined dose (RP2D) in the phase 2 portion. Pinometostat will continue as a continuous IV infusion through day 35. A bone marrow biopsy will be performed on day 8 to assess the single agent activity. On day 8, standard of care 7+3 with cytarabine and daunorubicin will be initiated. One re-induction attempt is permitted if no CR or CRi is achieved by day 21 (day 14 of 7+3). No further study treatments (e.g. consolidation or maintenance) are planned, and patients should be consolidated as per standard of care.

Phase: 1b, 2

SCHEMA

This study is a multi-site phase 1b/2 study designed to confirm a safe and tolerable dose of pinometostat and to gauge preliminary evidence of efficacy when given as lead-in prior to and contemporaneous with standard intensive induction therapy for newly diagnosed AML with MLL rearrangement. There will be a brief safety run-in phase exploring two dosing schemes, followed by a phase 2 efficacy expansion. The phase 2 expansion will use the higher dose-level of the two schedules if tolerated (see definitions below), otherwise, the lower dose-level if tolerated. The phase 1b/safety run-in portion will have a primary endpoint of Dose-limiting Toxicity (DLT; defined below), while the phase 2 portion will have a primary endpoint of complete remission attainment, and will gather additional laboratory correlative data.

[figure not shown]

Figure 1: Abbreviated Trial Schema (Depicting Initial Induction. Re-induction resets calendar; see details)

Phase 1b/safety run-in phase

The phase 1b portion will operate according to Figure 1. Up to two cohorts will be accrued in order to identify a maximum tolerated dose for expansion. Dose escalation will occur in the standard cohorts-of-3/3+3 design. With only two cohorts (dose levels), escalation stops after cohort 2; if 2-3/3 DLT are observed at dose level 1 (cohort 1), a safety review will be initiated to decide whether dose level reductions below the starting dose should be considered.

Phase 2/expansion phase

The phase 2 portion will use the maximum tolerated dose/schedule and accrue additional patients to gather preliminary evidence of efficacy. Patients will be treated in the same manner as in the phase 1b portion above, with the exception that only a single dose level/cohort will be expanded.

Re-induction

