1.2 Secondary Objectives

- 1.2.1 To observe and record anti-tumor activity. Although the clinical benefit of pinometostat has not been fully established, the intent of offering this treatment is to provide a possible therapeutic benefit, and thus the patient will be carefully monitored for tumor response and symptom relief in addition to safety and tolerability
- 1.2.2 Estimate biologic activity of 7 day window treatment of pinometostat monotherapy
- 1.2.3 Estimate the toxicity profile of pinometostat alone (week 1) and in combination with daunorubicin and cytarabine
- 1.2.4 Estimate event free and overall survival of patients with MLL rearranged acute myeloid leukemia after combination treatment with pinometostat, daunorubicin, and cytarabine
- 1.2.5 Estimate the early death rate (death \leq 30 days) of pinometostat, daunorubicin, and cytarabine
- 1.2.6 Determine the rate of MRD negativity by clinical flow cytometry on post-treatment recovery bone marrow

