3. PATIENT SELECTION

3.1 Eligibility Criteria

- 3.1.1 Patients must have histologically confirmed Acute Myeloid Leukemia by World Health Organization (WHO) criteria. Patients with treatment-related acute leukemia are eligible if they do not exceed lifetime anthracycline doses as outlined below.
- 3.1.2 Presence of a cytogenetic rearrangement of *KMT2A* (MLL) by interphase Fluorescent *in-situ* Hybridization (FISH).
- 3.1.3 Patients must have previously untreated (with exception of hydroxyurea for count control, or ATRA for acute promyelocytic leukemia (APML) that was initially suspected but later ruled out) AML by World Health Organization (WHO) criteria. Treatment with hydroxyurea for count-control of hyperproliferative disease is permitted before and during treatment with pinometostat and chemotherapy.
- 3.1.4 Age ≥ 14 years at time of screening, although individual sites may further restrict age eligibility in accordance with local IRB and hospital policy.
- 3.1.5 ECOG performance status ≤ 2 (Karnofsky $\geq 60\%$; see Appendix A).
- 3.1.6 Patients must have adequate organ function at the time of eligibility screening as defined below:
- Total bilirubin $\leq 1.5 \times$ institutional ULN, unless elevated due to Gilbert syndrome, hemolysis, or leukemia
 - AST(SGOT)/ALT(SGPT) $\leq 2.5 \times$ institutional ULN, unless due to leukemia in which case $< 5 \times$ ULN
 - Creatinine $\leq 1.5 \times$ institutional ULN
OR
 - Glomerular filtration rate (GFR) ≥ 60 mL/min/1.73 m² for patients with creatinine levels above institutional normal.
 - Coagulation: PT and aPTT $\leq 1.5 \times$ ULN (both)

 - Human immunodeficiency virus (HIV)-infected patients on effective antiretroviral therapy with undetectable viral load within 6 months are eligible for this trial.
 - If evidence of chronic hepatitis B virus (HBV) infection, HBV viral load must be undetectable on suppressive therapy if indicated.
 - If history of hepatitis C virus (HCV) infection, must be treated with undetectable HCV viral load.

- For pediatric patients, a serum creatinine based on age/gender as follows:

| Age | Maximum Serum Creatinine (mg/dL) | |
|------------------|----------------------------------|--------|
| | Male | Female |
| 10 to < 13 years | 1.2 | 1.2 |
| 13 to < 16 years | 1.5 | 1.4 |
| ≥ 16 years | 1.7 | 1.4 |

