4.4 General Guidelines

Following registration, patients should begin protocol treatment as rapidly as possible, but in no more than 7 days. Issues that would cause treatment delays should be discussed with the Principal Investigator. If a patient does not receive protocol therapy following registration, the patient's registration on the study may be canceled. The Study Coordinator should be notified of cancellations as soon as possible.

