11. STUDY CALENDAR

Baseline evaluations are to be conducted within 1 week prior to start of protocol therapy. In the event that the patient's condition is deteriorating, laboratory evaluations should be repeated in order to decide if therapy should be continued.

Table 11.1: Initial treatment plan.

| | Pre-Study / Screening | Wk 1 | Wk 2 | Wk 3 | Wk 4 | Wk 5 | Off Study ^c | Long Term Follow-Up ^f |
|---|-----------------------|------|----------------|------|------|----------------|------------------------|----------------------------------|
| Pinometostat | | A | A | A | A | A | | |
| Cytarabine | | | B | | | | | |
| Daunorubicin | | | C | | | | | |
| Informed consent | X | | | | | | | |
| Demographics | X | | | | | | | |
| Medical history | X | | | | | | | |
| Concurrent meds | X | X | X | X | X | X | | |
| Physical exam | X | X | X | X | X | X | X | |
| Vital signs | X | X | X | X | X | X | X | |
| Height and Weight | X | X | X | X | X | X | X | |
| Performance status | X | | | | | | | |
| CBC w/diff, plts, PT/INR, aPTT | X | X | X | X | X | X | X | |
| Serum chemistry ^a | X | X | X | X | X | X | X | |
| EKG (as indicated) | X | | | | | | | |
| Echocardiogram/MUGA | X | | | | | | | |
| Adverse event evaluation | | X | X | X | X | X | | |
| B-HCG | X ^b | | | | | | | |
| Bone marrow aspiration and biopsy | X | | X | | X | X ^d | | |
| Bone marrow metaphase karyotype | X | | X | | X | X ^d | | |
| Bone marrow MLL (KMT2A) translocation by FISH | X | | X | | X | X ^d | | |
| Immunophenotyping (BM and PB) | X | | X | | | X ^d | | |
| Differentiation analysis | X | | X ^e | | | X ^d | | |
| Comprehensive mutational profile | X | | X ^e | | | X ^d | X | |
| Survival | | | | | | | | X ^f |

A: Pinometostat: Dose as assigned; weeks 1-5, days 1-35
B: Cytarabine: 100 mg/m² continuous IV infusion; week 2, days 8-14
C: Daunorubicin: 60 mg/m² IV; daily days 8-10 of week 2
a Albumin, alkaline phosphatase, total bilirubin, bicarbonate, BUN, calcium, chloride, creatinine, glucose, uric acid, LDH, phosphorus, potassium, total protein, SGOT [AST], SGPT [ALT], sodium.
b. Serum or urine pregnancy test (women of childbearing potential).
c. Off-study evaluation.
d. And at count recovery in week 5 or beyond
e. Day 8 of week 2, and at relapse (if applicable)

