12. MEASUREMENT OF EFFECT

Although the clinical benefit of this drug has not yet been established, the intent of offering this treatment is to provide a possible therapeutic benefit, and thus the patient will be carefully monitored for tumor response and symptom relief in addition to safety and tolerability. Patients with measurable disease will be assessed by standard criteria. For the purposes of this study, patients should be re-evaluated daily during their admission for induction chemotherapy and then no less than every four weeks, depending on clinical context, after discharge.

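### The week-1 blast endpoint in section 9.3 is measured from screening, up to 7 days before the first dose, so up to half of the interval can be drug-free and the estimate of single-agent activity can be biased in either direction

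*Combined protocol and SAP*

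**What the plan says.** Secondary objective 1.2.2 reads: "Estimate biologic activity of 7 day window treatment of pinometostat monotherapy". The item in section 9.3 that serves it is: "Differential blast counts between screening and day 8 will be analyzed using lab evaluation of complete blood counts and differential". Section 9.3 does not say whether blasts are absolute or a percentage, and it does not require the day-8 count to come before chemotherapy.

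The timing comes from other sections:

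- Section 11: "Baseline evaluations are to be conducted within 1 week prior to start of protocol therapy". In Table 11.1 screening is a separate column from week 1.
- Section 4.4: "Following registration, patients should begin protocol treatment as rapidly as possible, but in no more than 7 days".
- Treatment-plan summary ahead of the Schema: "Pinometostat will be given IV starting on day 1". The same summary starts 7+3 on day 8.
- Section 3.1.3: "Treatment with hydroxyurea for count-control of hyperproliferative disease is permitted before and during treatment with pinometostat and chemotherapy".
- Section 6.1.8 lets 7+3 begin before day 8 when disease cannot be controlled in the first week.

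Other looks at single-agent activity are planned. The treatment-plan summary says: "A bone marrow biopsy will be performed on day 8 to assess the single agent activity". Sections 5.1 and 5.3.1 add exploratory mass cytometry (CyTOF) and a morphology differential, each taken at screening and day 8.

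**The concern.** The objective is about a 7-day window on drug, but the endpoint covers a longer interval that starts at a different point for each patient. The trial is single-arm, so within-patient change is the activity estimate itself, and nothing in 9.3 removes or reports change that occurred before dosing.

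The protocol gives reason to expect such change. Section 2.1 describes AML as rapidly progressive, and hydroxyurea is allowed before treatment to bring counts down. Growth before day 1 would mask activity, and a hydroxyurea response before day 1 would look like activity. In both cases the error depends on how long the patient waited between the screening sample and the first dose, which is partly administrative.

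At stake is the reading of the monotherapy window, which is the reason for delaying 7+3 to day 8. A pre-dose count that was never drawn cannot be recovered at analysis.

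**Working it through.** The documents give no effect size, power or sample size for this endpoint, so there is no stated figure to reproduce.

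**Step 1: share of the interval without drug.** Let g be the days from the screening count to the first dose, 0 to 7 under section 11. Pinometostat alone runs for 7 days before day 8. The drug-free share is g / (g + 7).

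| g (days) | Calculation | Drug-free share |
|---|---|---|
| 0 | 0/7 | 0% |
| 1 | 1/8 | 12.5% |
| 3 | 3/10 | 30% |
| 7 | 7/14 | 50% |

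This step uses only the documents' own limits.

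**Step 2: untreated growth before dosing (illustration).** Assume exponential change in absolute blasts with doubling time T, and a true day-1-to-day-8 ratio of 0.50. The observed ratio is 0.50 × 2^(g/T). At g = 7:

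| T (days) | 2^(7/T) | Observed ratio | Reads as |
|---|---|---|---|
| 5 | 2.64 | 1.32 | 32% rise |
| 7 | 2.00 | 1.00 | no change |
| 10 | 1.62 | 0.81 | 19% fall |
| 14 | 1.41 | 0.71 | 29% fall |
| 20 | 1.27 | 0.64 | 36% fall |
| 40 | 1.13 | 0.56 | 44% fall |

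The gap matters as much as T. With T = 7, the observed ratio is 0.55 at g = 1, 0.67 at g = 3 and 1.00 at g = 7. Three patients with the same response to drug would thus show falls of 45%, 33% and 0%.

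**Step 3: hydroxyurea before dosing (illustration).** Assume hydroxyurea halves blasts every h days before day 1, and blasts then stay flat from day 1 to day 8. The observed ratio is 0.5^(g/h). At g = 7 it is 0.20 for h = 3, 0.50 for h = 7 and 0.71 for h = 14. A drug with no effect would appear to cut blasts by 80%, 50% or 29%.

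**Step 4: does the plan already supply a better baseline?** Not reliably. Table 11.1 marks a CBC with differential in week 1 but fixes neither the day nor a pre-dose draw. Section 12 says "patients should be re-evaluated daily during their admission for induction chemotherapy", which does not promise a differential every day. Section 11 asks for laboratory tests to be repeated in a deteriorating patient, but does not make the repeat the baseline. By contrast, 9.3 does count progression-free survival from the first day of study treatment.

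**Step 5: the day-8 end.** Section 5.3.1 requires the day-8 marrow for mass cytometry to be taken before 7+3. Section 9.3 sets no such condition on the blood count, although 7+3 starts the same day.

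**The case against.** The strongest reply has five parts.

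1. *Other measures are planned.* This stands. A reader might infer that the blood blast count is the only planned measure of single-agent activity. It is only the sole such endpoint listed in 9.3, since the day-8 marrow, mass cytometry and morphology are planned too. They do not cure the problem: cytometry and morphology also compare with screening, and Table 11.1 schedules no marrow between screening and week 2.

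2. *The sizes are assumed.* This stands. No doubling time, expected effect or actual gap is given, the largest figures use the maximum gap, and section 4.4 asks for prompt treatment. If blasts are meant as a percentage, the value is capped at 100% and the doubling model does not carry over. The drug-free share in Step 1 does not rest on these assumptions.

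3. *A pre-dose baseline leaves other confounding.* This stands. Hydroxyurea during days 1 to 7 and an early start of 7+3 both act after day 1, so they must be reported separately.

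4. *Change before dosing would not simply be credited to the drug.* This is right as a correction of direction. A reader might infer that the flaw flatters pinometostat. The documents do not support that, because growth and hydroxyurea pull in opposite directions.

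5. *The endpoint decides nothing.* This stands, and it limits the weight of the point. No test or threshold is attached, dose selection rests on DLTs, and the efficacy conclusion rests on CR/CRi.

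**Conclusion.** The concern holds in a limited form. Screening is the stated baseline for the only single-agent activity endpoint in 9.3, it may precede the first dose by up to 7 days, and up to 7 of the 14 days measured can therefore be drug-free. The resulting bias in the estimate for objective 1.2.2 can go either way and differs between patients. It is absent only where the screening count is taken just before the first dose or blasts do not change in between.

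The maximum share of 50% follows from the protocol's own windows. The observed ratios in Steps 2 and 3 rest on assumed exponential change, assumed rates and, except where stated, the maximum gap. They show what is possible, not what is likely.

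A reader might also infer that the trial's main conclusions are at risk. They are not: neither the Simon design for CR/CRi nor the 3+3 rules use this count. The change is worth making because it improves a stated secondary estimate at little cost and has to be in place before the samples are drawn.

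**What to change.** **In section 9.3:**

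- Define the baseline as the last CBC with differential before the first pinometostat dose. Define the endpoint as the within-patient change in absolute blood blasts from that count to the day-8 CBC drawn before the first 7+3 dose.
- Use the screening count only where no later pre-dose count exists. Report how many patients this affects and their gaps in days.
- Summarise on a scale that copes with zero counts, such as absolute change, or a log ratio with a stated offset. A plain log ratio is undefined for a patient with no circulating blasts at either time, including one who clears them by day 8.
- Report results with and without patients who received hydroxyurea in days 1 to 7 or began 7+3 before day 8. For early starters no day-8 count can precede 7+3, so state in advance which count is used. Leaving them out is not neutral, because they start early when disease is uncontrolled; both sets of results are needed.

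**In Table 11.1:** time the existing week-1 CBC before the first pinometostat dose and the existing week-2 CBC on day 8 before 7+3.

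**Cost:** a small calendar clarification as well as the wording in 9.3, with hydroxyurea dates available for the analysis (section 6.4 already requires all concurrent drugs on the case report form). No added visit or test is needed. Some patients may still lack a later pre-dose count and keep the screening value. Mass cytometry and morphology would keep their screening baseline, so the screening-to-dose gap should be reported beside those results too.

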2.4 Rationale

MLL-r AML occurs more commonly in younger AML patients (15% among patients less than age 60) compared to older patients (only about 2% among patients aged greater than 60 years) and as a high-risk disease subset is typically treated with 7 + 3 induction, 0-1 cycles of consolidation (depending on donor status), and then allogeneic stem cell transplant. Patients who relapse, or patients who were primary refractory, have leukemias enriched for mutations in pathways (e.g. RAS/ERK, or PTPN11/STAT) that render the cells insensitive to inhibition of Syk signaling or epigenetic silencing by DOT1L inhibition. Accordingly, we have observed a higher response rate among front line patients compared to relapsed or refractory patients in response to SYK inhibition (unpublished observation), and would anticipate a similar scenario with DOT1L inhibition. Overall, relapsed and refractory patients represent a small heterogeneous population with induction failure or relapse after transplant, in both cases likely enriched for mutations conferring resistance to targeted therapies, and do not represent an ideal population in which to administer a targeted therapy due to the risk of missing an agent with up-front activity. For any agent, the heterogeneous and poorly understood relapsed/relapsed population represents a very challenging drug development and registration strategy, whereas development could potentially be pursued more systematically and rationally in newly diagnosed patients.

To further understand newly diagnosed MLL-r patients, we examined records from 118 historical cases of MLL-r AML treated on CALGB/Alliance cooperative group clinical trials. Patients less than age 60 have only a 64% CR rate with 7+3 induction/5+2 re-induction (if necessary; *Mims et al: publication in preparation*). This CR rate is significantly below what can be achieved by other subgroups, and patients who fail to achieve CR are less likely to move to transplant and overall are more likely to die sooner of their disease. Therefore, there is a significant opportunity to show clinical benefit in this previously untreated patient population by adding another agent to 7+3 chemotherapy.

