Length of study treatments

Study treatment will end after either 35 days (first induction) or 28 days (with calendar reset to day 1 on the first day of 5+2 in second induction attempt) of pinometostat. Patients should then receive standard of care consolidative therapy including allogeneic bone marrow transplant, but these are not considered study treatments. No specific consolidation is mandated.

Follow-up period

Patients will be followed until the soonest of death, alternative leukemia therapy (i.e. for relapsed or refractory disease; this is excluding the planned consolidation that may directly follow the study treatment) initiated, enrollment on another therapeutic clinical trial, bone marrow transplantation, voluntary or involuntary withdrawal from study (see section 6.5) or lost to follow-up.

Toxicity assessment

All patients who receive any amount of the study drug will be evaluable for toxicity. Toxicity will be graded and reported according to the Common Terminology Criteria for Adverse Events (CTCAE) Version 5. The CTEP Active Version of the CTCAE is identified and located on the CTEP website at http://ctep.cancer.gov/protocolDevelopment/electronic_applications/ctc.htm. All appropriate treatment areas should have access to a copy of the CTEP Active Version of CTCAE.

It is recognized that drug-related toxicity in this population may be difficult to ascertain, given the aggressive hematologic disease. Investigators will attempt to assign attribution of toxicities to each drug if possible. Toxicity attributed to any of the three agents will be considered dose limiting. Dose limiting toxicity will be divided into non-hematologic and hematologic toxicity.

Dose-limiting toxicity

Definitions of dose-limiting toxicities are in section 6.2.

Patients who receive at least 1 dose of pinometostat during cycle 1 will be considered to be evaluable for toxicity/DLT and will not be replaced during the dose escalation phase of the trial unless the PI determines that further additional patients at that dose level are required for safety purposes; the context in which DLTs are noted (before or after the introduction of 7+3) will be considered in this decision. Patients with transient liver function test abnormalities (AST, ALT, bilirubin, or alkaline phosphatase) that resolve to < grade 1 within 5 days will not be considered DLT. Infection will not constitute DLT unless it is felt that the infection resulted from

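### The PFS rule in section 9.3 does not exempt planned consolidation from censoring, so read literally it censors responders because they are in remission and conflicts with sections 9.1 and 6.6

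*Combined protocol and SAP*

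**What the plan says.** Section 9.3 defines the endpoint as "Progression free survival for all patients, defined as the time from the start of study treatment until progression or death, whichever occurs earliest". Its censoring rule is "Patients will be censored at earliest of loss to follow-up, allogeneic stem-cell transplantation, or initiation of other anti-leukemia therapy when in remission". For estimation it says "The Kaplan-Meier method will be used to estimate time to progression and overall survival"; I take the first of these to mean the PFS just defined.

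On care after induction, the treatment plan summary at the front of the protocol says "patients should be consolidated as per standard of care". Section 9.1 (Length of study treatments) says "Patients should then receive standard of care consolidative therapy including allogeneic bone marrow transplant, but these are not considered study treatments", and adds "No specific consolidation is mandated". Section 2.4 gives the usual path for this disease as 7+3, then "0-1 cycles of consolidation (depending on donor status), and then allogeneic stem cell transplant".

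Two other passages list what ends follow-up. Section 9.1 (Follow-up period) names alternative leukemia therapy but qualifies it: "this is excluding the planned consolidation that may directly follow the study treatment". Section 6.6 names transplant and therapy given in remission, and limits the latter to investigational treatment, including cell therapy. Both end follow-up at transplant. Footnotes f and g of the study calendar nevertheless require contacts for up to 5 years that record survival, subsequent therapy and transplant. Relapse is not on that list.

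**The concern.** Standard consolidation is leukemia treatment, is not study treatment, and is given in remission. On the plain words of 9.3, a responder is therefore censored when it starts. Only responders can be censored this way, so the censoring carries information about outcome, whereas Kaplan-Meier assumes that it does not. Each censored responder is in effect represented afterwards by whoever remains at risk, a group in which patients without remission are over-represented.

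PFS is the only time-to-event measure of disease control that 9.3 defines, and the nearest to the event-free survival named in objective 1.2.4. Two analysts could apply 9.3 in good faith, one importing the exemption from 9.1 and one not, and report clearly different curves from the same data.

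**Working it through.** **1. The three rules side by side**

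| Place | Purpose | Therapy in remission | Transplant |
|---|---|---|---|
| 9.3 | PFS censoring | any, no exemption | censors |
| 9.1, Follow-up period | end of follow-up | planned consolidation excluded | ends follow-up |
| 6.6 | end of follow-up | investigational only | ends follow-up |

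The three agree on transplant and disagree on planned consolidation.

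**2. What the documents supply.** They state no PFS figure. They give a maximum N of 31 and CR rates of 65% (null) and 85% (alternative). The exact two-stage binomial for 13/8 and 31/23 gives a type I error of 0.0951, as stated, and power of 0.904 against the stated 90%. The rates imply 31 × 0.65 ≈ 20 to 31 × 0.85 ≈ 26 responders. Consolidation rate, transplant rate and their dates are not given.

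**3. Mechanism, by hand (assumed data, every responder consolidated).** There are 25 responders censored on days 50-70 and six failures with events on days 30, 45, 80, 100, 150 and 200. Kaplan-Meier is 30/31 × 29/30 = 0.935 after day 45. Only 4 remain at risk at day 80: 0.935 × 3/4 = 0.70. Then × 2/3 = 0.47, × 1/2 = 0.23, and 0 at day 200, although 25/31 = 81% were event-free when censored.

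**4. Size (assumed inputs).** CR p = 0.80. Remission is at day 35, with a 12-month median to relapse or death after it. Failures' events come at 20 days plus an exponential with mean 87 days (mean 107 days, about 3.5 months). Relapse counts as an event, and later therapy does not change the hazard. Six months is 182.6 days.

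- Responders: S_R(t) = exp(−ln 2 × (t − 35)/365.25), so S_R(60) = 0.954, S_R(120) = 0.851, S_R(182.6) = 0.756.
- Failures: S_F(t) = exp(−(t − 20)/87), so S_F(60) = 0.631, S_F(120) = 0.317, S_F(182.6) = 0.154.
- True 6-month PFS = 0.8 × 0.756 + 0.2 × 0.154 = 0.64.

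If a fraction u of responders is censored on day c, Kaplan-Meier tends to

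S(c) × [(1−u)p·S_R(t) + (1−p)·S_F(t)] / [(1−u)p·S_R(c) + (1−p)·S_F(c)], with S(c) = p·S_R(c) + (1−p)·S_F(c).

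S(60) = 0.889 and S(120) = 0.744. The simulation has 31 patients, with consolidation spread over days 50-70 or transplant over days 90-150.

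| Censored at | u | Formula | Simulated 6-month PFS | At risk at 6 months (responders) |
|---|---|---|---|---|
| Consolidation | 100% | 0.889 × 0.0308/0.1263 = 0.22 | 0.24 | 1.0 (0) |
| Consolidation | 90% | 0.889 × 0.0913/0.2026 = 0.40 | 0.41 | 2.9 (1.9) |
| Consolidation | 70% | 0.889 × 0.2122/0.3552 = 0.53 | 0.53 | 6.6 (5.6) |
| Transplant only | 60% | 0.744 × 0.2727/0.3357 = 0.60 | 0.61 | 8.4 (7.5) |
| Transplant only | 90% | 0.744 × 0.0913/0.1314 = 0.52 | 0.55-0.56 | 2.8 (1.9) |
| Transplant only | 100% | 0.744 × 0.0308/0.0634 = 0.36 | 0.48 | 1.0 (0) |

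The formula puts all censoring on one day and assumes many patients. It is rough where few remain at risk, so the simulated column is the one to use.

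**5. Sensitivity.** If failures' events are exponential from day 0 with mean 3.5 months, the consolidation rows become 0.31, 0.45 and 0.56 against 0.64. With a 30-day delay plus a mean of 2.5 months they become 0.20, 0.38 and 0.52 against 0.63. At the plan's own CR rates (failures' median 2 months, consolidation at month 1.5-2.5, half of responders transplanted), 70-100% uptake gives 0.22-0.40 against 0.54-0.55 at CR 65%, and 0.33-0.57 against 0.67-0.68 at CR 85%.

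**The case against.** The best reply is that 9.3 is shorthand for 6.6. Both list transplant, therapy in remission and loss to follow-up, and 9.1, in the same chapter, exempts planned consolidation outright. On that reading only transplant censors, and at 60% transplanted the bias is about 0.03. The binomial standard error at 0.64 with 31 patients is √(0.64 × 0.36/31) = 0.086, so 0.03 is about a third of it. This is a fair account of what the authors may have meant. It does not remove the defect: 9.3 is the only PFS censoring rule, and it contains neither qualifier.

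A reader might infer that nearly every responder leaves the curve within weeks and that only failures remain. The documents do not support that. They give no uptake or dates, mandate no specific consolidation, and make the number of cycles depend on donor status. At 70% consolidated, or with transplant-only censoring at 60%, most patients at risk at 6 months are responders. The strong form needs near-universal early consolidation, or is approached with about 90% early transplant.

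Censoring at transplant is also partly a choice of estimand, namely disease control before transplant. That is a reason to report both curves, not to drop this one. Finally, no test or historical comparison of PFS is planned; the historical hypothesis concerns CR only.

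**Conclusion.** The concern holds as a conflict between 9.3 and its companion rules in 9.1 and 6.6, with a downward bias in PFS if 9.3 is followed literally. Under the assumptions shown, 6-month PFS is understated by about 0.11 at 70% uptake (0.64 − 0.53), 0.23 at 90% and 0.40 at 100%. If consolidation is exempt and only transplant censors, the shortfall is about 0.03 at 60% transplanted, 0.08-0.09 at 90% and 0.16 at 100%. The direction requires only that responders have a lower event rate than non-responders. The size rests on assumed uptake, dates and hazards. The effect is confined to a descriptive secondary endpoint: the CR/CRi test does not use this rule, and 9.3 attaches no such rule to OS. The wording should be corrected, but the trial's main conclusion does not depend on it.

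**What to change.** In 9.3, state that planned standard consolidation directly following study treatment is not a censoring event for PFS, in line with 9.1 and 6.6. This is a wording change and needs no new data.

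Also report PFS not censored at transplant beside the transplant-censored curve, and label both. The uncensored curve includes the effect of transplant, so neither replaces the other. It costs more than wording. Relapse status and date must be added to the contacts in study calendar footnotes f and g. The end of follow-up at transplant in 6.6 and 9.1 must be reconciled with those footnotes, which continue contact for up to 5 years. The same edit should say whether hematologic relapse, defined in 12.2 separately from progressive disease in 12.1, counts as a PFS event.
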